- (1) Cuff closure (compared between test and reference groups) will be assessed (yes or no) by an independent surgeon at one and six weeks, as well as at six months. Fisher's Exact Test will be used to assess possible significance of a difference in cuff closure scores between test and reference groups.
- (2) Cuff healing (compared between test and reference groups), will be assessed (yes or no) by an independent surgeon at six weeks and six months. Fisher's Exact Test will be used to assess possible significance of a difference in healing scores between test and reference groups.
- (3) The percentage of subjects experiencing implant (either clip or suture) passing by six-weeks and by six-months post-operative will be compared between test and control groups using Fisher's Exact Test.
- (4) Frequency of implant passing events determined to be associated with an Adverse Event will be reported through six weeks.

Safety Analysis:

The Safety population will be the analysis population for all safety analyses.

[figure not shown]
Primary Safety Endpoint:

The primary safety endpoint, frequency of vaginal cuff dehiscence, will be reported through six weeks.

Secondary Safety Endpoints:

- (5) The number of adverse events and serious adverse events as well as the proportion of subjects with adverse events, will be summarized by treatment arm, severity, and relatedness to device. Adverse events will be coded using the validated MedDRA system. By-subject listings will be provided for all safety data. Incidence of adverse events will be compared using Fisher's Exact test to assess possible significance of adverse event rate.
- (6) Comparison (test to reference group) of non-increase in subject dyspareunia scores from baseline to 6-months post-operative will be assessed using Fisher's Exact Test.
- (7) Comparison (test to reference group) of non-increase in subject pain scores from baseline to 6-months post-operative will be assessed using Fisher's Exact Test.

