Study recruitment is designed to avoid any potential coercion. Potential subjects will have decided with their doctor to undergo minimally invasive hysterectomy prior to discussing possible participation in this trial. Once a potential candidate has been successfully pre-screened, the informed consent process will be conducted by a study investigator or coordinator other than the potential subject's doctor.

Study enrollment takes place during surgery. Intra-operative enrollment criteria are designed to specifically evaluate closure of the vaginal cuff during laparoscopic hysterectomy, the step Zip-stitch™ is designed for. Subjects who may have unforeseen complications during the anesthesia or colpotomy process for example, are not intended for treatment and their procedure should continue according to standard of care.

Study randomization will take place via blinded, variable block size randomization envelopes stratified by site. Subjects will be blinded to the treatment they receive, but as the operating surgeon cannot be blinded to the treatment provided, this study cannot be fully double-blinded. Every effort will be made to minimize opportunities for unblinding during post-operative data collection. In particular data collection will be performed by a different investigator surgeon without access to the blinded to treatment assignment, including through the electronic data capture system.

Data unblinding will take place after completion of six-week follow-up. This enables reporting of the primary study endpoints and most secondary study endpoints. The data collected at the 6 and 12-month follow-up visit and telephone call are limited to dehiscence, pain, dyspareunia, and adverse events. Adverse events are likely to have significant clinical sequelae, and therefore not likely to be forgotten. Pain and dyspareunia are evaluated based on experience in the time frame of the call, and therefore are not affected by recall bias. No statistical comparisons are being made using 12-month data.

Protocol QD-PRO-045 Rev 005

Some secondary endpoints evaluate incidence and rate of various events; others compare test and reference groups. Comparisons will be made using two-sided Fisher's Exact Tests. Secondary endpoints are not powered to reach statistical significance but are intended to provide additional information and indicate possible safety and efficacy trends.

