6.3 MEASURES TO MINIMIZE BIAS: RANDOMIZATION AND BLINDING

Variable block size randomization will be employed to assign a vaginal cuff closure method to each subject. At the time of enrollment and after confirmation of intraoperative eligibility, a subject will be randomly assigned treatment (cuff closure) with the test device (Zip-stitch™) or reference device (VICRYL™). This assignment will be provided via sponsor provided randomization envelopes broken down in 2:1 variable block sizes and stratified by site. Treatment allocation blocks will vary from three to six subjects and will be split 2:1 test to reference assignment. This method helps safeguard against a simple randomization generating a smaller than intended test or reference group.

Subjects will be blinded to the cuff closure method they receive during surgery. Because operating surgeons cannot be blinded to the treatment they are providing, this trial cannot be completely double-blinded. Every effort will be made to minimize bias in post-operative data collection. Data collection will be performed by an investigator without access to the blinded to treatment assignment. Treatment assignment will be recorded at the time of procedure in the electronic data capture system. After this point, the investigator collecting follow-up data will be blinded to medical records and treatment group. The operative surgeon cannot be blinded as the performed treatment. They will be available during follow-up as needed but will not participate in data collection for patients that they provided treatment.

Database lock and data un-blinding will take place after completion of the last six-week follow-up visit. Subjects will still participate in the 6 and 12-month visit and extension period call, but data will be unblinded. The data collected at the 12-month telephone visit are limited to pain, dyspareunia, and adverse events. Adverse events are likely to have significant clinical sequelae, and therefore not likely to be forgotten. Pain and dyspareunia are evaluated based on experience in the time frame of the call, and therefore are not affected by recall bias.

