8.3 ADVERSE EVENTS AND SERIOUS ADVERSE EVENTS

8.3.1 DEFINITION OF ADVERSE EVENTS (AE)

Adverse event means any untoward medical occurrence associated with the use of an intervention in humans, whether or not considered intervention-related (21 CFR 312.32 (a)).

Adverse Event details will be classified and reported by a study investigator and confirmed by the study PI. Classifications of adverse events are described below. Clip passing, by itself, is *not* an adverse event.

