8.3.3 CLASSIFICATION OF AN ADVERSE EVENT

Adverse events will be coded using a validated medical dictionary (MedDRA - Medical Dictionary for Regulatory Activities, (McLean, VA)).

SEVERITY OF EVENT

The following guidelines will be used to describe the severity of an adverse event.

- Mild Events require minimal or no treatment and do not interfere with the participant's daily activities.
- **Moderate** Events result in a low level of inconvenience or concern with the therapeutic measures. Moderate events may cause some interference with functioning.
- **Severe** Events interrupt a participant's usual daily activity and may require systemic drug therapy or other treatment. Severe events are usually potentially life-threatening or incapacitating. Of note, the term "severe" does not necessarily equate to "serious".

RELATIONSHIP TO STUDY INTERVENTION

The clinician's assessment of an AE's relationship to study intervention (Zip-stitch™ system or VICRYL™) is part of the documentation process, but it is not a factor in determining what is or is not reported in the study. If there is any doubt whether a clinical observation is an AE, the event should be reported. All AEs must have their relationship to study agent assessed. For all collected AEs, the clinician who examines and evaluates subjects will determine the AE's likely causality based on temporal relationship and his/her clinical judgment. The causality will be graded using the categories below:

- **Definitely Related** There is clear evidence to suggest a causal relationship, and other possible contributing factors can be ruled out. The clinical event, including an abnormal laboratory test result, occurs in a plausible time relationship to study intervention administration and cannot be explained by concurrent disease or other drugs or chemicals. The response to withdrawal of the study intervention should be clinically plausible.
- Probably Related There is evidence to suggest a causal relationship, and the influence of other
 factors is unlikely. The clinical event, including an abnormal laboratory test result, occurs within
 a reasonable time after administration of the study intervention, is unlikely to be attributed to
 concurrent disease or other drugs or chemicals, and follows a clinically reasonable response on
 withdrawal.

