8.3.4 TIME PERIOD AND FREQUENCY FOR EVENT ASSESSMENT AND FOLLOW-UP

Any medical condition that is present at the time that the subject is screened, but does not exclude said subject, will be considered as baseline and not reported as an AE. However, if the study subject's condition deteriorates at any time during the study, it will be recorded as an AE.

Changes in the severity of an AE will be documented to allow an assessment of the duration of the event at each level of severity to be performed. AEs characterized by surgeon to be intermittent, or having distinct episodes, require documentation of onset and duration of each episode.

An investigator will record all reportable events with start dates occurring any time after informed consent is obtained until the last day of study participation, AEs occurring before, but not resolving by, the last day of study participation will be followed for an additional 7 (for non-serious AEs) or 30 days

Protocol QD-PRO-045 Rev 005

(for SAEs) after. If such an SAE is determined to be probably or definitely related to the investigational device, then it may be followed for longer.

At each study visit, the investigator will inquire about the occurrence of AE/SAEs since the last visit. Events will be followed for outcome information until resolution or stabilization. All AEs will be followed to adequate resolution.

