9.4.5 ANALYSIS OF SECONDARY SAFETY ENDPOINTS

The Safety population will be the analysis population for all safety analyses.

Secondary Endpoint (5) Comparison of incidence of adverse events.

Data collection: Adverse Events will be tabulated for both the test and reference groups. All AEs and SAEs will be MedDRA-coded and summarized by treatment arm. In addition, the number and proportion of AEs and SAEs will be calculated for each group. For each MedDRA-coded medical term, the proportion of subjects who experience at least one of the following will be reported and compared.

Adverse event

- Adverse event related to treatment
- Serious adverse event
- Serious adverse event related to treatment
- Adverse event leading to study discontinuation
- Serious adverse event leading to study discontinuation

Classification of AEs will also be presented and compared. Events will be reported by MedDRA system organ class and preferred term. Adverse Events will be compared by severity and device relatedness between the test and reference groups.

Acceptance Criteria: There is no defined endpoint acceptance criteria for the comparison of adverse events.

Statistical Analysis Method: A two-sided Fisher's Exact Test will compare (test versus reference) rate of incidence of adverse events by six months post-operative. Assessment of this is independent of the primary study endpoints.

Secondary Endpoint (6) Comparison (test to reference group) of non-increase in subject dyspareunia scores from baseline to 6-months post-operative.

Data collection: Individual subject dyspareunia will be assessed using the relevant sexual discomfort module of the validated Female Sexual Function Index (FSFI). Higher scores indicate good sexual function with little or no sexual discomfort, and lower scores indicate poor sexual function with higher levels of sexual discomfort. Scores of zero indicate no sexual activity and will not be included in comparison of non-increase in dyspareunia.

Acceptance Criteria: A subject level failure is defined as a decrease in sexual function score (signifying an increase in dyspareunia). Endpoint success is defined as the same or lower rate of FSFI score decrease in the test group at six months when compared to the reference group at six months.

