9.4.7 PLANNED INTERIM ANALYSES

There is no interim analysis planned. Primary endpoint analysis and reporting will take place after completion of all six-week follow-up. This report will be considered the final study report and will completely assess the primary study endpoint. There will be additional supplementary reports with follow-up endpoint analysis at 6 and 12-months. See study design rationale for additional details.

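### The recall rationale for late adverse-event collection does not cover mild events, and the only dated general AE comparison pools the blinded first six weeks with a long last interval whose blinding is stated inconsistently

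*Combined protocol and SAP*

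**What the plan says.** **Recall.** Section 6.3 states that "Adverse events are likely to have significant clinical sequelae, and therefore not likely to be forgotten". There the sentence follows a description of the 12-month telephone call. Section 4.2 uses the same sentence more widely, directly after saying that "The data collected at the 6 and 12-month follow-up visit and telephone call are limited to dehiscence, pain, dyspareunia, and adverse events". So 4.2 is where the argument reaches the six-month visit.

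**What counts as an AE.** Section 8.3.1: "Adverse event means any untoward medical occurrence associated with the use of an intervention in humans". The mild grade in 8.3.3 reads: "Events require minimal or no treatment and do not interfere with the participant's daily activities". Secondary endpoint 5 counts women with AEs of any grade.

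**When women are asked.** Section 8.3.4: "At each study visit, the investigator will inquire about the occurrence of AE/SAEs since the last visit". The visits are at one week, six weeks and six months (8.1), and 8.2 allows for unscheduled visits.

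**The test.** Section 9.4.5 specifies a two-sided Fisher's exact test of the "rate of incidence of adverse events by six months post-operative". The synopsis gives the test no time point: "Incidence of adverse events will be compared using Fisher's Exact test to assess possible significance of adverse event rate". Section 3.2(5) gives none either.

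**The report.** Section 9.4.7 says of the six-week report: "This report will be considered the final study report and will completely assess the primary study endpoint". Section 4.1 sends later data to supplemental reports.

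**Blinding at six months.** The synopsis (study duration), 4.2 and 6.3 unblind after the last six-week visit. The synopsis (study description) lists the six-month visit among the blinded ones, and 8.1 unblinds only when all six-month visits are complete.

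**The concern.** The recall argument works for events that leave a mark. It does not work for an untreated event that did not disturb a woman's day and that she is first asked about some 20 weeks after the previous visit. Section 2.3.4 reports no major AEs in earlier use of the device but lists fevers, urinary tract infections and post-operative vaginal bleeding. Events short of major ones are therefore what the sponsor has actually seen.

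The six-month test adds two kinds of data together. The first six weeks have two scheduled enquiries, at most about five weeks apart, under blinding that no section disputes. The rest has one scheduled enquiry after a much longer gap, possibly with assignments known. Relatedness is graded by the examining clinician using judgement (8.3.3), and treatment-related AEs are one of the compared categories (9.4.5), so knowledge of assignment could affect grading as well as reporting. If the late interval is recorded differently in the two arms, the cumulative figure cannot show it. The report that the plan calls final has no specified general AE comparison from the better-protected period.

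**Working it through.** **Plan's own figures.** The enrolment target reproduces: 35 / (1 − 0.10) = 38.9, so 39 test; 39 / 2 = 19.5, so 20 reference; total 59. The documents give no AE rate, AE time course or power for endpoint 5.

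**Calendar share of the last enquiry.** Take six weeks as 42 days and six months as 365.25 / 2 = 182.6 days.
- Interval before the six-week visit: 42 − 7 = 35 days.
- Interval before the six-month visit: 182.6 − 42 = 140.6 days, about four times as long.
- Share of the six-month window: 140.6 / 182.6 = 77%.
- Across the visit windows in 8.1 (six-week visit ± 5 days, six-month visit ± 7 days): (175.6 − 47) / 175.6 = 73% to (189.6 − 37) / 189.6 = 80.5%.

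**Share of events.** Suppose the AE rate in the first six weeks is k times the later rate. The share of events falling in the first six weeks is 42k / (42k + 140.6).

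| k (assumed) | Share of events by six weeks |
|---|---|
| 1 | 23% |
| 2 | 37% |
| 3.35 | 50% |
| 5 | 60% |
| 10 | 75% |

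The break-even is 140.6 / 42 = 3.35. Above it, most events come from the first six weeks. The documents do not say which side of it the trial lies on.

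**How many six-month visits follow unblinding, on the 6.3 rule.** Assume uniform enrolment over the planned three to five months.
- Three months (91.3 days): unblinding at day 91.3 + 42 = 133.3, before the earliest six-month visit. All six-month visits come after unblinding.
- Five months (152.2 days): unblinding at day 194.2. Women enrolled before day 194.2 − 182.6 = 11.6 are seen first, 11.6 / 152.2 = 8% (about 16% at the extremes of the visit windows). The other 92% or so come after unblinding.
- On the 8.1 rule, none does.

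**What a six-week test could show.** Two-sided Fisher's exact test at 0.05, 39 against 20, exact enumeration, assumed reference rate 20%: power is 27% against a test rate of 40%, 56% against 50% and 81% against 60%. The comparison would be descriptive, as the plan already says of its secondary endpoints (4.2, 9.2).

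**The case against.** Much can be said for the plan, and several stronger readings fail.

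- **A reader might infer that no safety comparison exists at six weeks.** That is wrong. Section 3.1 compares dehiscence, the primary safety endpoint, between arms to six weeks. Section 9.4.4 compares AE-associated implant passing through six weeks. The synopsis and 3.2(5) leave the general AE test undated, and 4.2 expects six-week unblinding to allow most secondary endpoints to be reported. What is missing is a general AE comparison dated to six weeks.
- **A reader might infer that the regulator sees only the six-week report.** Section 3 says six-month data may support clearance, and the synopsis plans a further submission after later follow-up.
- **A reader might infer that the six-month test rests mainly on the late enquiry.** That is shown for calendar time only. The test also includes the two earlier enquiries and unscheduled visits, and it follows major surgery, so early events may dominate.
- **A reader might take the six-month visit as unblinded.** The sections conflict. Those that unblind speak of the data; none says that women are told their assignment. Follow-up data are collected by someone other than the person who performed the closure (8.1), and an independent monitor adjudicates safety events (10.1.5). This protects classification, but it cannot recover events that were never reported.
- **A reader might want a size for the bias.** If 40% of each arm had an AE by six weeks, and the late enquiry drew a first AE from 15% of the rest in one arm and 30% in the other, the totals would be 0.40 + 0.60 × 0.15 = 49% and 0.40 + 0.60 × 0.30 = 58%. Nothing in the documents supports that doubling. Even then, Fisher's test at 39 against 20 would reject only about 7% of the time, against about 3% with equal rates. The example shows the mechanism and is not an expected effect.
- **Making six weeks the main comparison has a cost.** Clips are absorbed over five to eight months (synopsis), and a granuloma was reported at six months in earlier use (2.3.4). Late device events should not be demoted.

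All of these objections stand. They leave intact the mismatch between the recall claim and the mild grade, the absence of a dated six-week general AE comparison, and the conflict over blinding.

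**Conclusion.** The point holds in limited form. The recall rationale in 4.2, and its repeat in 6.3, does not fit the protocol's own AE definition and mild grade. Endpoint 5 has one dated general comparison. It mixes a clearly blinded period with an interval that fills about three-quarters of the window by calendar time and whose blinding the protocol states both ways. The six-week report, called final, has no specified general AE comparison.

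The 73% to 81% range rests only on the visit schedule. The share of events, and the size and direction of any bias, cannot be derived from the documents. Endpoint 5 has no acceptance criterion and no power, so what is at stake is a blurred descriptive safety comparison rather than a changed trial conclusion. The correction is worth making because it is cheap and uses data already collected.

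**What to change.** 1. In 9.4.5, endpoint 5, add a between-arm comparison of women with any AE, and of women with any device-related AE, through the six-week visit, and report it in the six-week final report.
2. Keep the six-month cumulative comparison with equal standing, and show it also by interval: 0 to 6 weeks, and 6 weeks to 6 months.
3. In 4.2 and 6.3, limit the claim about recall to severe or serious events.
4. Reconcile the statements on unblinding in the synopsis (study description and study duration), 4.2, 6.3 and 8.1, so that the blinding status of the six-month visit is unambiguous.

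Cost: wording changes, one extra table and one extra comparison that is unpowered and not adjusted for multiplicity, and should be labelled descriptive. Sample size, visits and data collection do not change.

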6.4 STUDY INTERVENTION COMPLIANCE

Protocol adherence is the responsibility of all investigator and will be regularly monitored by a study monitor in accordance with Sponsor clinical monitoring standard operating procedures. Any deviation from study protocol will cause a protocol deviation to be logged in the protocol deviation form on the electronic data capture system. All protocol deviations will be reported to the study sponsor and to required regulatory bodies in accordance with GCP.

6.5 CONCOMITANT THERAPY

For this protocol, a prescription medication is defined as a medication that can be prescribed only by a properly authorized/licensed clinician. Medications to be reported in the Case Report Form (CRF) are concomitant prescription medications, over-the-counter medications and supplements.

